To fill this gap, we have developed a first-of-its-kind school-based intervention for SGM youth, Proud & Empowered! (P&E). The multi-level program was developed over the last 9 years through (a) psychometric, developmental, and acceptability studies funded by the NIH, foundations (Zumberge), and intramural sources; (b) a collaboration with three SGM youth dropin centers, more than 100 SGM youth, and a dozen academic and clinical experts; and (c) an exploratory study (R21MD013971) to assess the feasibility and preliminary efficacy of the intervention. Given encouraging findings, we now propose to employ a large-scale randomized controlled trial (RCT) with 24 schools in Los Angeles to establish program efficacy. At intervention sites (n = 12), after the 10-session small group portion of the intervention with SGM youth is completed, peer allies (who are identified through a popular opinion leader model) are invited to participate in 4-session leadership program focused on changing SGM-related school climate. This is followed by student-led implementation of environmental change strategies at the school level focused on key domains of school climate described by Thapa et al. (2013): safety, relationships, teaching and learning, and institutional environment. At the SGM student

level, analysis will focus on the hypothesized mechanism of change (minority stress) and key behavioral health outcomes (depression, anxiety, PTSD, suicidality, substance use).

Change in school climate will also be assessed qualitatively using content analysis and observational methods in the intervention and post-intervention years. Our specific aims are to:
1) Determine participant-level efficacy of the intervention in an RCT with 24 schools, 2)
Determine the schoolwide intervention effects on (a) reporting of minority stress and behavioral health outcomes among all SGM students and (b) perceptions of school climate (norms, attitudes, beliefs, bullying behaviors toward SGM youth, policies) among all students, and 3)
Examine factors that may affect intervention success (e.g., fidelity of implementation, barriers or facilitators to implementation, school or student characteristics) to prepare the intervention for future dissemination.

Participants

1. Inclusion Criteria:

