All measures are valid and reliable psychometric tests. As this is a quantitative study, all measures are closed-ended and survey-based. Information on each specific measure is as follows:

Sexual Minority Adolescent Stress Inventory: 54-item survey across 10 domains of minority stress. Assesses experiences of minority stress among adolescents. Each statement reflects past-30-day thoughts, feelings, and situations a person may have experienced.

Beck Anxiety Inventory: 21-item self-report assessment of anxiety symptoms.

PTSD Checklist for DSM-5 (PCL-5): 20-item self-report assessment of post-traumatic stress disorder (PTSD) symptoms which addresses all 20 DSM-5 symptoms of PTSD.

Beck Depression Inventory: 21-item self-report assessment of depression symptoms and severity of depression.

Adapted CSSRS Suicide Questions (Columbia Suicide Severity Rating Scale): Six items assessing current suicidality that were adapted from the longer, treatment-based Columbia Suicide Severity Rating Scale

Youth Risk Behavior Survey Substance Use Questions: Measures individual's usage of various substances in their lifetime and within the past 30 days as well as the ways in which individuals have used marijuana, tobacco, or nicotine in the past 30 days.

Coping Strategies Inventory: 16-item assessment measuring specific coping strategies people use in response to stressful events with each item assessing components of Problem Solving, Cognitive Restructuring, Social Support, Expressed Emotions, Problem Avoidance, Wishful Thinking, and Social Withdrawal.

LGBTQ+ Coping: 20-item assessment measuring ways individuals cope with stressors that are specifically related to being LGBTQ+ over the past 3 months.

California Healthy Kids Survey General Bullying and Gender Identity/Sexual Orientation-Based Harassment Module: Assesses students' perceptions of harassment experiences on school campus among the general student population in addition to bullying and harassment experiences on school campus specific of students who identify as, or are perceived to be, lesbian, gay, bisexual, transgender, questioning, or gender nonconforming.

Civic Measurement Models: Measures competency for civic action, political efficacy and participatory citizen to assess young people's perceived ability to engage in civic action (e.g., organize a meeting), express their political voice (e.g., sign a petition), and critically analyze political messages.

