Data Analysis

A series of analyses will be conducted to thoroughly investigate the program effects and its fidelity on outcomes of interest. First, a cluster-randomized repeated measures ANOVA will be used to examine the intervention effects on minority stress, behavioral health outcomes, and coping skills among the cohort of SGM adolescents who participate in the small group intervention and their control-school counterparts. Second, qualitative content and observational analysis by study staff will be used to conduct a baseline policy scan in the intervention year, inform Make Space participant activities, and evaluate change in policies over the course of the year.

Data Protection

All survey data will be coded using a unique code selected by each participant. Coded data will be held separately from all identifying data, such as recruitment information. Assent/consent will be collected in a separate survey though RedCap in order to keep as little identifying information about LGBTQ+ participants and POL participants as possible. All contact information used for recruitment be destroyed at the conclusion of the study. Downloaded data will be stored on dual-authentication and password-protected computers. Only the PI and authorized study staff will have access to survey data.

Dissemination of Findings

The proposed study plans to consistently disseminate findings from study data and – if warranted – to provide broad access to the final intervention program. The dissemination plan aims to inform research on minority health, risk and protective factors among SGM youth. Research findings will also be disseminated through peer-reviewed journals, national conferences, and relevant compendiums of intervention research if possible (e.g., Cochrane).

Data Safety Monitoring Board (DSMB)

The DSMB will meet quarterly during the first year of the project and annually thereafter and is composed of recognized experts in SGM clinical ([name]) and adolescent research ([name]; [name]) with no direct involvement in the study. The DSMB will be charged with ensuring the highest standards for participant safety and data

quality. Initially, the board will review the study design, instruments and methods, recruitment criteria, intervention plan, and data analytic plan. It will provide recommendations to safely achieve our goals. Subsequent meetings will focus on monitoring study participant enrollment, safety, and protocol adherence (*see DSMB and Letters of Support*).

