A series of analyses will be conducted to thoroughly investigate the program effects and its fidelity on outcomes of interest. First, a cluster-randomized repeated measures ANOVA will be used to examine the intervention effects on minority stress, behavioral health outcomes, and coping skills among the cohort of SGM adolescents who participate in the small group intervention and their control-school counterparts. Second, the school-wide intervention effects of reporting minority stress and behavioral health outcomes among all SGM students across all schools and school climate outcomes among all students across all schools will utilize multilevel regression analyses with mediation and/or moderation, to understand how participant-level and school-level characteristics influence these outcomes. Third, qualitative content and observational analysis by study staff will be used to conduct a baseline policy scan in the intervention year, inform Make Space participant activities, and evaluate change in policies over the course of the year.

Data Protection

All survey data will be coded using a unique code selected by each participant. Coded data will be held separately from all identifying data, such as recruitment information. Assent/consent will be obtained verbally in order to keep as little identifying information about LGBTQ+ participants and allies as possible. All contact information used for recruitment be destroyed at the conclusion of the study. Downloaded data will be stored on dual-authentication and password-protected computers. Only the PI and authorized study staff will have access to survey data. California Healthy Kids Survey data will anonymous third-party data shared by WestEd., and will be analyzed and held separately from all other study data.

Dissemination of Findings

The proposed study plans to consistently disseminate findings from study data and – if warranted – to provide broad access to the final intervention program. The dissemination plan aims to inform research on minority health, risk and protective factors among SGM youth. Research findings will also be disseminated through peer-reviewed journals, national conferences, and relevant compendiums of intervention research if possible (e.g., Cochrane).

References:

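### The efficacy analysis gives eight outcomes equal standing (seven in the Combined protocol and SAP), with no primary outcome, wave, significance level or multiplicity rule named

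*Protocol*

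**What the plan says.** The Protocol's Objectives section describes a "large-scale randomized controlled trial (RCT) with 24 schools in Los Angeles to establish program efficacy". The same section says that analysis at student level will focus on "the hypothesized mechanism of change (minority stress) and key behavioral health outcomes (depression, anxiety, PTSD, suicidality, substance use". That makes six outcomes.

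Data Analysis in the Protocol sets out the quantitative efficacy analysis in one sentence: a cluster-randomized repeated measures ANOVA that "will be used to examine the intervention effects on minority stress, behavioral health outcomes, and coping skills among the cohort of SGM adolescents". The Combined protocol and SAP has the same sentence, beginning "First, a cluster-randomized repeated measures ANOVA will be used to examine the intervention effects on minority stress".

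For coping, the Protocol's Instrumentation section lists two scales. One is the Coping Strategies Inventory, a "16-item assessment measuring specific coping strategies people use in response to stressful events". The other is LGBTQ+ Coping, a "20-item assessment measuring ways individuals cope with stressors that are specifically related to being LGBTQ+ over the past 3 months". The Combined document lists only the first. Minority stress is measured by the SMASI (Sexual Minority Adolescent Stress Inventory), a "54-item survey across 10 domains of minority stress".

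Surveys are taken in September, November and May. The Protocol's Methods section adds a second randomization of the intervention schools, to P&E alone or P&E plus Make Space. The Combined document does not describe it. In neither document does Data Analysis rank the outcomes, choose a wave, give a significance level or state a multiplicity rule.

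**The concern.** A trial meant to establish efficacy needs a stated result that would count as success, and a known probability of reaching it by chance. Here every outcome has the same standing. Nothing in the two documents would prevent one significant scale out of seven or eight from being presented as the efficacy finding, or the lead outcome from being settled after results are known. The chance of a false claim then depends on how many outcomes are examined and how closely they correlate, and the plan does not limit it. This cannot be repaired credibly once outcomes have been seen by arm.

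**Working it through.** The documents state no error rate or sample-size calculation, so there is no figure of the plan's own to reproduce.

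**Inputs from the documents**
- Outcomes in the Protocol: 1 (minority stress) + 5 (depression, anxiety, PTSD, suicidality, substance use) + 2 (coping) = 8.
- Outcomes in the Combined document: 1 + 5 + 1 = 7.
- The bullying module and the civic measures are not counted, because the ANOVA sentence does not name them.
- Schools: 24, of which 12 are intervention schools. Groups are limited to 12 students.

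**Assumptions (not in the documents)**
- Two-sided 0.05 per test.
- One score per instrument and one test per outcome.
- A common correlation between test statistics, taken from 0 to 0.9.
- Each test holds its own level, which requires clustering by school to be handled properly.

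**Independent outcomes:** P(at least one significant) = 1 − (1 − 0.05)^k.
- k = 8: 1 − 0.95^8 = 0.337.
- k = 7: 1 − 0.95^7 = 0.302.
- k = 8 at 0.01 per test: 1 − 0.99^8 = 0.077.

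**Correlated outcomes, k = 8** (normal simulation with 400,000 draws; school-level t tests, 12 v 12 schools, 22 df, 40,000 simulated trials):

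| Correlation | Any significant result | School-level t tests | False benefit only |
|---|---|---|---|
| 0 | 34% | 33.5% | 18.4% |
| 0.3 | 30% | 29.9% | 15.2% |
| 0.5 | 25% | 25.3% | 12.5% |
| 0.7 | 19% | 19.6% | 9.5% |
| 0.9 | 11.8% | not run | 5.9% |

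A mixed pattern (five distress outcomes at 0.6, the two coping scales at 0.5, all other pairs at 0.2) gives 27%. For comparison, a single two-sided 0.05 test gives 5% for any significant result and 2.5% for a false benefit.

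The ANOVA's test might be an arm-by-time test with more than one degree of freedom. The independent figure is then unchanged, because it depends only on the level and the count.

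**Price of the remedies.** Take 12 v 12 schools of 12 students, 80% power and 22 df. The detectable effect in SD units is (t for the level + t for the power) × √(2 × [1 + 11 × ICC] / 144). At an assumed ICC of 0.05 the square root is √(2 × 1.55 / 144) = 0.147.
- One primary test at 0.05: (2.074 + 0.858) × 0.147 = 0.43 SD.
- At 0.05/8 = 0.00625, the first Holm step over eight outcomes: (3.023 + 0.858) × 0.147 = 0.57 SD.
- For ICC from 0.01 to 0.10 the ranges are 0.36 to 0.50 SD and 0.48 to 0.66 SD.

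These values ignore dropout and any gain from baseline adjustment, so only the comparison between them matters here.

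**The case against.** Several points on the other side have force.

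- **One in three.** A reader might state this as the plan's false-positive rate. It is the top of a range: it needs eight independent outcomes and a 0.05 level that neither document states. Distress measures taken in the same youth are unlikely to be independent, so a range is the honest statement. The Combined document also supports seven outcomes, not eight.
- **Benefit or harm.** If the worry is a false claim of efficacy, only the beneficial direction counts. That gives about 12% to 18% for correlations of 0.5 to 0, which is lower but still well above 2.5%.
- **More tests.** A reader might multiply further by the two follow-up waves, the SMASI domains or the active arms. Such tests would raise the rate, but the plan does not describe them. A repeated measures ANOVA handles the waves jointly, and the planned comparison is of participants with students in control schools.
- **No decision rule.** Neither document says that one significant scale would establish efficacy, and it would be wrong to attribute that rule to the sponsor. They are silent, and the silence leaves the rule open.
- **Other sources.** The Protocol carries a registration number and says that the DSMB reviews the analytic plan. Either might fix a primary outcome, but neither record is available here. The finding is limited to what these documents name.
- **Minority stress as the implied primary.** Objectives calls it the hypothesized mechanism and sets it apart from the key behavioral health outcomes. That does not designate it as primary.

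**Conclusion.** The concern holds, with its size given as a range. These documents leave the efficacy claim without error control: eight outcomes in the Protocol, seven in the Combined protocol and SAP, all of equal standing. Under two-sided 0.05 and one test per outcome, the chance of at least one false-positive result with eight outcomes is 19% to 34% for correlations of 0.7 to 0. With seven independent outcomes it is 30%. At a correlation as high as 0.9 it is still more than twice the nominal 5%. The level, the single score per instrument and the correlations are assumptions. A level of 0.01 per test would bring the independent figure for eight outcomes down to about 8%. The documents do not support the view that the rate is one in three or higher for the plan as written.

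**What to change.** In Data Analysis, in both documents:

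1. Name one primary outcome and one primary wave before outcome data are examined by arm, and document that the choice was made without sight of those data. Survey and consent forms labelled Y2 in the Protocol suggest that earlier data may already exist, so that record matters.
2. Test the primary at two-sided 0.05, and state that both randomized active arms are pooled against control.
3. The choice of primary belongs to the sponsor. A natural candidate is the SMASI score at May, with its scoring defined. May is the last wave, and it follows Make Space training in the schools that receive it. Schools given P&E alone never receive that training. A behavioral health outcome is equally consistent with Objectives.
4. Test the remaining key outcomes (depression, anxiety, PTSD, suicidality, substance use, and SMASI if it is not primary) as a Holm-adjusted secondary family. With five outcomes the first step uses 0.05/5 = 0.01. State whether this family is tested only after a significant primary result. If it is tested regardless, the overall error bound is 0.05 + 0.05 = 0.10.
5. Label coping scales, SMASI domains and November results as supportive.
6. If no single primary is acceptable, apply Holm across all the outcomes.
7. Claim efficacy only on the primary test or on outcomes that survive Holm.

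**Cost.** The changes are wording plus the record in item 1. The primary test gives up no power relative to an unadjusted 0.05 test. Holm across all eight outcomes would be dearer: at its first step the detectable effect rises from about 0.43 to 0.57 SD under the assumed ICC of 0.05. The sponsor also gives up the right to claim efficacy from an isolated unadjusted p-value below 0.05 on a secondary scale.

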Although the impetus for P&E is to reduce victimization and bullying experiences, increased visibility due to participation could result in increased targeting. This may not only occur for SGM-identified participants, but also for POL allies, who may be targeted by association. Given this, our recruitment and consent processes for both SGM and POL students will discuss this potential risk of participation. As part of our study intake procedures, we educate participants on existing policies and what procedures are in place to protect them, including whom they should contact and what kinds of support they can expect. During the intervention, facilitators check in weekly with participants about safety concerns and refer to school-based supports, as necessary, following existing school protocols. Youth may also discontinue participation, if desired, at any time. Finally, our DSMB will meet regularly to review all procedures, including potentially trial stopping factors such as increased victimization. These protocols allow us to monitor student experiences regardless of whether victimization experiences are related to study participation or other extraneous factors.

Suicide and Emergency Standards of Procedure

Potential Emergencies:

For purposes of monitoring and reporting adverse events, the following NIH definitions will be used:

Adverse Event (AE): any untoward medical occurrence that may present itself during treatment or administration of an intervention, and which may or may not have a causal relationship with the treatment. Adverse events could arise from the study (e.g., breach of confidentiality) or could arise due to the population under study (e.g., a participant becomes upset answering sensitive questions).

Serious Adverse Event (SAE): Any medical occurrence that results in death; is life-threatening; requires inpatient hospitalization or prolongation of existing hospitalizations; creates persistent or significant disability/incapacity, or a congenital anomaly/birth defect. Such an event could include suicidal ideation or attempted drug overdose or withdrawal, etc.

There are five possible sources of AE which we can foresee based on our prior work with sexual minority adolescents:

- 1. Emotional distress due to discomfort with the survey questions. Although rare, we recognize that some youth may find personal questions distressing to answer.

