- 2. Accidental disclosure of confidential material. It is possible that despite our carefully constructed privacy safeguards that there could be accidental disclosure of confidential information.
- 3. Imminent threat to self. It is possible that youth will express suicidal intent. See detailed notes at the end of this document for specific suicide protocols for study surveys.

- 4. Imminent threat to others. It is possible that youth will express the intention to harm someone else or someone else's property.
- 5. Detection of previously undisclosed child or elder abuse. It is possible that youth may disclose abuse to our research staff during the surveys or intervention.

If a participant discloses possible self-harm, suicidal ideation, homicidal ideation, or the sexual or physical abuse of a minor or elder during the intervention or research study, research staff will immediately contact the PI ([name]) for consultation in appropriately handling the potential emergency. In our prior experience, fewer than 1% of interviews required enacting the emergency protocol.

The study staff will assess the situation and, if need be, inform and consult [name] (research manager) about the case. [name] is an experienced clinical Master of Social Work and has overseen fieldwork and handled emergency situations in clinical settings. The study staff facilitating the training will also be a licensed and/or masters-level mental health clinician (LCSW, LPCC, LMFT) with experience in working with LGBTQ+ youth. Project administrator and/or study facilitator will immediately notify the PI ([name]) of any adverse or serious adverse event

All study team members will complete emergency procedures training prior to contact with study participants. In the event of an emergency situation, a debrief with all of the research staff will occur to discuss what happened, what worked well, and what to know for next time. All study team members will be instructed on how to implement emergency procedures in situations without alarming the subjects (e.g., by teaching study staff to remain calm and to proceed with the emergency procedures in the same calm and forthright manner that they have been conducting the rest of the study). Study staff will also be trained in the following emergency response protocol that includes:

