- (i) Staff will be taught to stay with the subject for as long as it takes for them to have made contact with the manager and to be directed as to what the next step needs to be. If the staff is directed to call the psychiatric emergency services for a 5150 evaluation or for other emergency or police services, they will stay with the participant until the emergency team arrives.
- (ii) There will be a 15-minute maximum wait for the Project Administrator to respond to the study staff; after 15 minutes, the study staff will then call the site coordinator or school counselor.
- (iii) During the waiting period, study staff will be trained to provide a simple explanation to the participant that they need to contact a supervisor team member to make a plan to provide referrals for the participant and to ensure a safety plan. They will be trained to provide reassurance and support for the participant, letting them know that they will remain with the participant until they are able to make a good plan for how to address the emergency issue. They should also answer any questions the participant may have in a simple and straightforward fashion. If they are uncertain about a response, they should state that the first step is for both of them to get more information from the supervisor about

what would be helpful to make sure the participant's needs are met. Since they have already conducted the identified safety screening algorithm, and determined that a consultation with a supervisor is appropriate, the staff will be trained to not continue an assessment of the emergency issue (such as suicidality) until the information is reviewed with the PI, project administrator, and/or study facilitator.

- (iv) Study staff will remain with the participant, explaining the procedure to consult with the Project Administrator and PI in situations when a participant is distressed and/or if there is a concern about safety issues. If there is a waiting period, the staff will provide reassurance and support to the participant in order to reduce any potential distress or concern. In the rare situation in which a participant may be highly agitated, raising an immediate safety concern for the participant, study staff, or other individuals, study staff will call 911 and request emergency services.

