Additional protocol for identifying suicidality in survey participants: Because the intervention participant surveys assess for recent suicidal ideation, intent, plans, and attempts, we will implement protocols to immediately identify youth who report suicidal risk and connect them to the school counselor. The participant survey will be programmed in Qualtrics and the final screen for all youth will instruct them to: "Let the research team know you've finished the survey to receive your gift card. Code: complete." This will allow the team to verify survey completion and give the student their gift card. The Qualtrics survey will be programmed to include the youth's score on the suicide measures with the "Code: complete" message, such that students with no risk will get "Code: complete 1" and those with highest risk will get "Code: complete 5." This code is designed to not catch the attention of the student, but still allow the research staff to note the student's risk level, and then confidentially connect the student to the school counselor for further help outside of the intervention session.

References:

- 2. D'Augelli A, Grossman, Arnold H. Disclosure of sexual orientation, victimization, and mental health among lesbian, gay, and bisexual older adults. *Journal of interpersonal violence*. 2001;16(10):1008-1027.

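### Suicide risk reported on the survey reaches staff only through a code on the last screen, so an unfinished or unshown survey raises no flag

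*Protocol*

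**What the plan says.** Under Suicide and Emergency Standards of Procedure, the Protocol lists imminent threat to self among the foreseeable sources of adverse events and sends the reader elsewhere for the survey procedure: "See detailed notes at the end of this document for specific suicide protocols for study surveys". Those notes are the paragraph headed Additional protocol for identifying suicidality in survey participants.

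That paragraph states the aim: "we will implement protocols to immediately identify youth who report suicidal risk and connect them to the school counselor". It then gives the mechanism. "The participant survey will be programmed in Qualtrics and the final screen for all youth will instruct them to" report to the research team that they are done and collect a gift card. "The Qualtrics survey will be programmed to include the youth's score on the suicide measures with the" completion message, with 1 for no risk and 5 for the highest. Of the report to staff it says: "This will allow the team to verify survey completion and give the student their gift card". The code is meant to be unobtrusive to the student but readable by staff, who then make a confidential link to the counselor.

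The Combined protocol and SAP lists the same adapted Columbia items under Instrumentation but contains no procedure for acting on the answers.

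**The concern.** The promise and the trigger are tied to different events. The promise concerns a student who reports risk, which happens when the suicide items are answered. The trigger fires only when the student has reached the last screen and staff have seen it. Between those two moments the answer sits on the device and nothing in the survey procedure brings it to anyone's attention.

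This is a participant-safety matter, not an error of inference. The cohort is largely minors, parental permission is waived, and the Protocol's own Background stresses raised suicidality in this population. The link from survey to counselor therefore carries real weight. Stopping early is also foreseeable. The Protocol allows students to discontinue at any time, and its first listed source of adverse events is distress at survey questions: "some youth may find personal questions distressing to answer". It prefaces that by calling such reactions rare.

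**Working it through.** The documents state no figure on this point and no formula applies. The check is whether any other provision carries a survey answer to staff when the last screen is not reached or not shown.

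1. **Completion check and gift card (the suicidality paragraph).** Staff use the code to confirm completion, so a missing code may be noticed, and the gift card rewards finishing. No step is written for a survey that was started but produced no code.
2. **Disclosure response (Suicide and Emergency Standards of Procedure).** This begins when a participant discloses risk and sets out what staff then do. It does not say how an answer on a self-administered survey becomes known to staff.
3. **Distress procedure (item iv of the same section).** Staff stay with a distressed participant and consult the Project Administrator and PI. It is not limited to one arm or to spoken disclosure, so it is directly relevant to a student who stops because of distress. It depends on staff seeing the distress.
4. **Screening algorithm (item iii).** The text reads "Since they have already conducted the identified safety screening algorithm", but the algorithm is described nowhere in the documents. It cannot be counted as a second survey trigger.
5. **Counselors (item vi, and Recruitment).** Counselors are on site, and students who express interest meet one privately before selection. A counselor therefore knows the student, but is not told of an answer on an unfinished survey.
6. **Weekly check-ins (Data Safety Monitoring Board section).** "facilitators check in weekly with participants about safety concerns and refer to school-based supports", but only during the intervention. They are verbal and not prompted by survey answers. The ten weekly sessions run from September to about November, so they do not cover the May survey. Control students complete surveys only (Methods) and have none.
7. **Data access (Data Protection).** Access to survey data is restricted to the PI and authorized staff. No live alert or same-day review is set.

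None of the seven closes the gap. The two ways of falling into it behave differently:

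- **Stopping after the suicide items.** The importance of this depends on where those items sit. Item order is in a survey attachment that was not supplied. If they come last, early stopping matters little.
- **Finishing but leaving without showing the screen.** This does not depend on item order. LGBTQ Youth Procedures allows surveys on cell phones; whether these may be the student's own is not stated.

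**The case against.** The strongest reply is that the gap is narrow in practice. To leave without showing the screen, a student must forgo the gift card and get past staff who are confirming completion, on a school site, in a cohort of at most 12. A visibly distressed student falls under item iv. The Protocol calls survey distress rare and reports that fewer than 1% of interviews in prior work needed the emergency protocol. Unsupplied attachments or staff training may already contain the missing step.

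Much of this stands as to frequency. The 1% figure, however, is neither a rate of unfinished surveys nor a rate of raised codes, so it does not size the gap. The remaining safeguards depend on staff noticing something or on the student speaking, whereas the survey exists partly to find risk that is neither visible nor voiced.

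Two stronger readings are tempting. A reader might infer that control students are outside the survey procedure, because the paragraph opens by referring to surveys of intervention participants. Its heading speaks of survey participants and its final-screen wording covers all youth, so the documents do not support that; control students lack the sessions and check-ins, not the code. A reader might also infer that control students, or the May sittings, are unsupervised. Nothing in the documents says staff are absent from any sitting.

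**Conclusion.** The gap in the written procedure is real and should be fixed. Followed exactly, the stated mechanism can miss a student who has already reported risk on the device. Confidence in that is high, because it rests on the text alone.

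Confidence does not extend to how often it would happen. Item order, the rate of unfinished surveys and the rate of raised codes are all absent, so no number of missed students can be derived. A reader might try to size the problem by counting planned survey sittings; that would measure opportunity, not missed flags.

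Nor do the documents support the reading that there is no safety net. Partial safeguards exist in both arms, and they are thinner for control students, who have no facilitator sessions or check-ins. The conclusion assumes that no unsupplied attachment or operating procedure already provides an alert or a check of unfinished surveys.

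**What to change.** Two changes to the suicidality paragraph:

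- Program Qualtrics to score the suicide items when they are submitted and make the 1-to-5 code available to staff then, as a staff-side alert keyed to the Unique ID or the device. A new conspicuous student-facing screen would undercut the aim of not drawing the student's attention.
- Require the existing staff at each sitting, in both arms, to account for every started survey before students leave, or otherwise the same day. This includes unfinished surveys and finished ones whose code was not shown.

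The scoring and the counselor referral stay as they are.

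The cost is a survey-programming change, a small monitoring task per sitting, and a few sentences of protocol text. There is also a limited privacy cost. A student who has already left can be reached only by matching the Unique ID to a name. LGBTQ Youth Procedures keeps such tracking for counting sessions attended, which control students do not have, and Waiver of Documentation of Consent presents the assent/consent form as the sole record tying names to LGBTQ status. The match should therefore be confined to that case and stated in both the protocol and the assent/consent form.
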